While sepsis and septic shock have an infectious origin, SIRS may also have non-infectious triggers such as cardiac surgery using the Cardiopulmonary Bypass (CPB), ex vivo heart/lung perfusion device, ECMO, and Mechanical circulatory Support. This is of particular interest for this report. SIRS, sepsis and septic shock have a mortality of an estimated 7, 16 and 40% respectively [22-30]. The new 2016 Sepsis-3 definition has two grades: sepsis and septic shock [31-34]. The previous sepsis definitions published in 1992 emphasized on the role of systemic inflammatory response syndrome (SIRS) as a key element of the sepsis definition.

However, evidence showed that SIRS criteria are non-specific and insensitive as predictor for sepsis related mortality, thus are not included in the most recent international sepsis definitions. The members of the Sepsis-3 taskforce suggested that sepsis should be considered in the event of an infectious process associated with an increase in SOFA score of two points or more. Patients with septic shock would be clinically identified by a vasopressor requirement to maintain a mean arterial pressure of 65 mmHg or greater, and serum lactate level greater than 2 mmol/l (>18 mg/dl) in the absence of hypovolemia. SIRS patients identified by fulfilling two or more of the four SIRS criteria. The two main therapeutic priorities include early identification of a potential infectious origin and hemodynamic stabilization of the patient. Other than the control of the primary site of infection, there is no causal treatment for sepsis, septic shock or SIRS [35-39].

In order to improve the results of ECMO and septic patients, various techniques used to reduce the systemic inflammatory response syndrome, immunocorrection, and others. Today, there are many ways to prevent the development of a systemic inflammatory response by removing leukocytes from the bloodstream by inserting a filter with a special screen into the perfusion circuit to remove leukocytes and prevent them from entering the systemic circulation [9].

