### Study Design

Study Type: Interventional (Clinical Trial)

Estimated Enrollment: 90 Participants

Allocation: randomized

Interventional Model: Parallel assignment

Masking: None (Open Label)

Experimental (subgroups)	Intervention / treatment (device)
Cytokine adsorber filter will be installed into the (hemodialysis or cardiopulmonary bypass (CPB) (15 patients on ECMO)	Cytokine adsorber is a biocompatible, high adsorptive polymer indicated in conditions where cytokine levels are extremely elevated.
Cytokine adsorber filter will be installed into the (hemodialysis or cardiopulmonary bypass (CPB) (15 patients with sepsis)	Cytokine adsorber is a biocompatible, high adsorptive polymer indicated in conditions where cytokine levels are extremely elevated.
Extracorporeal hemoperfusion cartridge will be installed into the (hemodialysis or cardiopulmonary bypass (CPB) (15 patients on ECMO)	Extracorporeal hemoperfusion cartridge is a biocompatible, high adsorptive polymer indicated in conditions where cytokine levels are extremely elevated.
Extracorporeal hemoperfusion cartridge will be installed into the (hemodialysis or cardiopulmonary bypass (CPB) (15 patients with sepsis)	Extracorporeal hemoperfusion cartridge is a biocompatible, high adsorptive polymer indicated in conditions where cytokine levels are extremely elevated.
Control (subgroups)	
No filter will be installed into the ECMO in	

this study group (15 patients)	
No filter will be installed into the patient with sepsis (15 patients)	

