#### Secondary outcomes

1. Ventilator free days (VFD) [Time Frame: 30 days]

Ventilator free days (VFD) in the first 30 days after randomization, where invasive mechanical ventilation (IMV), non-invasive ventilation (NIV) and ECMO are defined as ventilator days. VFD=0, if the patient dies in the first 30 days after randomization

2. Time to extubation from ventilation and explantation from ECMO [ Time Frame: 30 days ]

Time to extubation from ventilation and explantation from ECMO. Death under ventilation and/or ECMO will be analyzed as a competing event. The time will be censored at the time of last visit for surviving patients under ventilation and/or ECMO.

3. Difference of d-dimers [Time Frame: 24, 48, 72 hours]

Comparison to enrollment or between 3 groups at 24, 48, 72 h

4. Difference of Serum lactate [Time Frame: 24, 48, 72 hours]

Comparison to enrollment or between 3 groups at 24, 48, 72 h

5. SOFA-Score [Time Frame: 24, 48, 72 hours]

Sequential Organ Failure Assessment Score at 24, 48, 72 h (values from 6 to 24, where the higher values explain higher disease severity)

6. Serious adverse device effects [Time Frame: 30 days]

Serious complications or malfunctions related to the CytoSorb device

7. Adverse event of special interest: air in the ECMO system [Time Frame: 30 days]

- Unintended air in the ECMO system during operation of the device
- 8. Adverse event of special interest: blood-clotting in the ECMO system [Time Frame: 30 days]
  - Unintended blood-clotting in the ECMO system during operation of the device
- 9. Adverse event of special interest: bleeding complications [Time Frame: 30 days]
  - Major bleeding events

*Patient with septic shock*

- 1. Difference of Cytokine response [ Time Frame: 24-48 hours of septic shock ]
  - Cytokine response: Level of procalcitonin, Level of C-reactive protein, Level of interleukin-1, Level of interleukin-6, Level of interleukin-8, Level of interleukin-10, Level of Tumor Necrosis Factor-  $\alpha$  at 24, 48 hours.

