### Statistical studies

1) Statistical data processing

2) Comparison and analysis of source data

After data receiving, statistical analysis will be performed using SPSS Statistics software version 22. For quantitative data, the Mann-Whitney Yu non-parametric test and parametric t-test will be performed, and Fisher's non-parametric exact test and  $\chi^2$  parametric test will be performed for qualitative studies. Also, a logistic regression for categorical outcomes and a survival analysis (non-parametric Kaplan-Meier and parametric Cox regression) will be performed.

**Ages:**18 Years and older

**Sex:** All

**Accepts healthy volunteers:** No

Groups	Inclusion criteria	Exclusion Criteria:
ICU patients with ECMO	

• Hemodynamic support with vasopressors

• Procalcitonin level <math>\geq 1</math> ng/ml

• Invasive hemodynamic monitoring

• Written informed content

	

• age <math>< 18</math> years

• acute liver or kidney failure straight before transplantation

• the patient declines participating in the study

ICU patients with septic shock of medical origin	

• Signs of hypoperfusion: serum lactate <math>>2</math> mmol/L, low central venous oxygen saturation (ScvO2) (<math><70\%</math>) or high ScvO2 (<math>>85\%</math>), metabolic acidosis, oligo-anuria,

	

• Patients under 18 years

• Pregnancy (bHCG test positivity)

• Surgical intervention in context with the septic insult

	
high venous-to-arterial CO2-gap (dCO2 >6 mm Hg)
 
 
• Hemodynamic support with vasopressors
 
• Procalcitonin level <math>\geq</math> 1 ng/ml
 
• Invasive hemodynamic monitoring
 
• Written informed content
 
	
New York Heart Association IV heart failure
 
 
• Acute coronary syndrome
 
• Acute haematological malignancies
 
• Immunosuppression, systemic steroid therapy (>10mg prednisolon/day)
 
• Human immunodeficiency virus infection (HIV) and active AIDS
 
• Patients with donated organs
 
• Thrombocytopenia (<20.000/ml)
 
• More than 10%-of body surface area with third degree burn
 

--	---	--

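### Death on support is declared a competing event for time to extubation and explantation, but no cumulative-incidence method or rule for coding deaths is specified; if deaths are censored, the proportion weaned would be overstated

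*Combined protocol and SAP*

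**What the plan says.** Item 2 of the ECMO patients' list under Secondary outcomes is "Time to extubation from ventilation and explantation from ECMO [ Time Frame: 30 days", that is, 30 days. Two rules follow. On deaths: "Death under ventilation and/or ECMO will be analyzed as a competing event". On censoring: "The time will be censored at the time of last visit for surviving patients under ventilation and/or ECMO". Censoring is therefore reserved for patients who are alive and still supported.

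The Statistical studies section contains all the statistical methods. For time-to-event data it says "a survival analysis (non-parametric Kaplan-Meier and parametric Cox regression) will be performed" and stops there. It assigns neither technique to an outcome. It mentions no cumulative incidence function, Gray's test, Fine-Gray model or pair of cause-specific models, and it does not say how a death enters the analysis.

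The Study Design table plans "15 patients on ECMO" in each device arm and 15 ECMO patients without a filter. Two other outcomes register deaths. Ventilator-free days has the rule "VFD=0, if the patient dies in the first 30 days after randomization", and overall survival, under Other Pre-specified Outcomes, runs from randomization to death.

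**The concern.** The outcome definition and the methods section do not meet. A competing-event analysis is promised, but the listed techniques are those usually run with every non-event censored. Censoring a death treats the patient as someone who could still have been weaned later. One minus Kaplan-Meier then estimates weaning in a hypothetical setting without deaths, not the share of patients who come off support. A single Cox model for weaning with deaths censored compares weaning rates among patients still alive on support, which is also a different quantity from the chance of being weaned.

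What is at stake is the reported estimate. With 15 ECMO patients per arm, readers will rely on curves and percentages more than on p-values. A device arm that lost more patients on support could look as good as the control arm on this outcome. The trial is open label, so the method is better fixed before data are seen than chosen afterwards.

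**Working it through.** **No plan figure to reproduce.** The plan gives no event rates for this outcome. Its only size figure, "Estimated Enrollment: 90 Participants", agrees with 3 × 30 and 6 × 15 but has no stated derivation.

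**Inputs from the documents.** 30-day window; death on support is a competing event; only survivors on support are censored; 15 ECMO patients per arm. The only mortality figures are in section 3: "SIRS, sepsis and septic shock have a mortality of an estimated 7, 16 and 40% respectively". None is for ECMO patients and none is a rate of death on support.

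**Assumed inputs.** Constant hazards per day, a for weaning (extubated and explanted) and b for death on support, with no loss before day 30.

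**Formulas.**
- True proportion weaned by day 30 (cumulative incidence) = a/(a+b) × [1 − exp(−30(a+b))]
- Death on support by day 30 = b/(a+b) × [1 − exp(−30(a+b))]
- One minus Kaplan-Meier with deaths censored = 1 − exp(−30a)

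The third expression does not contain b, so the death-censored curve ignores the death rate altogether.

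**Step 1. Size of the overstatement, 5% assumed still supported at day 30.** Total hazard = −ln(0.05)/30 = 0.0999 per day, split in proportion to the final shares.

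| Death on support | a per day | True weaned | 1 − KM | Difference (points) |
|---|---|---|---|---|
| 20% | 0.0788 | 75% | 91% | 16 |
| 40% | 0.0578 | 55% | 82% | 27 |
| 60% | 0.0368 | 35% | 67% | 32 |
| 80% | 0.0158 | 15% | 38% | 23 |

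**Step 2. Two arms with the same weaning hazard, a = 0.0578.**
- Arm with b = 0.010: sum 0.0678; 1 − exp(−2.034) = 0.869. Weaned 0.0578/0.0678 × 0.869 = 74%; dead on support 13%.
- Arm with b = 0.042: sum 0.0998; 1 − exp(−2.994) = 0.950. Weaned 0.0578/0.0998 × 0.950 = 55%; dead on support 40%.
- One minus Kaplan-Meier in both arms: 1 − exp(−1.734) = 82%.

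A true gap of 19 points disappears.

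**Step 3. Sensitivity to the assumed hazards.** Fix a = 0.05 and choose b to give a set death rate. One minus Kaplan-Meier is 77.7% throughout.

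| Death on support | True weaned | Overstatement (points) |
|---|---|---|
| 7% | 73.7% | 4 |
| 16% | 68.3% | 9 |
| 20% | 65.9% | 12 |
| 40% | 52.8% | 25 |
| 60% | 37.9% | 40 |

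At 40% deaths, moving a from 0.03 to 0.08 moves the overstatement from 17 to 33 points.

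**Step 4. Effect on testing.** Two arms were simulated with a = 0.05 and deaths on support of 20% versus 40%. With 15 per arm (2,000 runs, nominal 5%), the death-censored log-rank test rejected in 6.2% of runs. A test keeping deaths at risk and unweaned to day 30 rejected in 8.6%. With 300 per arm (200 runs) the figures were 8.0% and 77.5%. At this trial's size the choice changes the estimate and hardly changes the test.

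**The case against.** A reader might infer that the plan commits itself to a biased analysis, so that weaning success will be overstated. The documents do not support that. Item 2 points the other way, since it names death as a competing event and limits censoring to survivors. The methods sentence is generic, and Kaplan-Meier and Cox may be meant for overall survival, where both are suitable. The bias is therefore conditional on deaths being censored.

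Nor are the named techniques unable to handle competing events. Separate Cox models for weaning and for death on support are an accepted analysis of cause-specific hazards. Kaplan-Meier with deaths held as unweaned to day 30 equals the cumulative incidence if nobody is lost earlier. This objection stands, but the plan states neither option, and the Cox pair alone gives no probability of weaning.

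A reader might also infer that the overstatement is always largest in the arm with most deaths. The first table shows otherwise: 32 points at 60% deaths but 23 at 80%. With equal weaning hazards it does grow with the death rate.

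Finally, the consequences are limited. One secondary outcome in one of the two patient groups is affected, and an arm with more deaths would not look equal across the whole report, because ventilator-free days and overall survival both register deaths. That also stands, and it sets the priority.

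**Conclusion.** The concern holds in conditional form. The mismatch between the outcome definition and the methods section is certain; the bias is not, because it depends on how deaths are coded. If Kaplan-Meier and Cox are meant for this outcome and used in the standard way, the analysis contradicts the outcome definition. If they are meant only for overall survival, this outcome has no stated method.

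Under constant hazards, censoring deaths would overstate weaning by 4 to 40 points in the main sensitivity range (weaning hazard 0.05 per day, 7% to 60% deaths on support), and would hide the 74% versus 55% difference completely. These sizes are illustrations. ECMO mortality, weaning rate and the share still supported at day 30 are all assumed, and the 40% for septic shock is only a reference point. The change should be made, as a correction to one secondary estimate; it does not threaten the trial's main comparison.

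**What to change.** In Statistical studies, add that time to extubation and explantation is analysed by Aalen-Johansen cumulative incidence by arm at 30 days, with Gray's test or Fine-Gray regression. State that death on support is coded as the competing event, and show its cumulative incidence beside that of weaning. Give cause-specific Cox hazard ratios for both weaning and death as support, to be read together. Keep Kaplan-Meier and the log-rank test for overall survival. If the stated SPSS version does not offer these procedures, name software that does.

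The cost is a few sentences and a little more analysis work, with no change to data collection or sample size. The reported proportion weaned will be lower than a death-censored Kaplan-Meier would show, and little power is gained.

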#### **4. Research methods and ethical issues**

Patients before implantation of ECMO and/or patients with sepsis will be enrolled in the study after giving a written, signed informed consent.

The participants will be randomized into 3 groups:

- **Intervention group #1** a cytokine adsorber will be used (30 patients): patients on ECMO – subgroup A; septic patients – subgroup B.
- **Intervention group #2** an extracorporeal hemoperfusion cartridge will be used (30 patients): patients on ECMO – subgroup C, septic patients – subgroup D.

- **Control group #3** without using extracorporeal adsorber (30 patients): patients on ECMO subgroup - E, septic patients - subgroup F.

The investigators will collect demographic, clinical and laboratory data about patients before, during and after the operation

The incidence of early cellular or humoral rejection, length of ventilation, ICU and hospital stay, the use of vasopressors and inotropes in the perioperative period and incidence of perioperative complications and survival will be documented.

The level of cytokines (IL-1, IL-6, IL-8, IL-10, tumor necrosis factor-alfa) and complements before, during and after the use of ECMO, patients with sepsis will be determined if the investigators find relevant difference between the two groups in clinical variables.

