## Outcome Measures

### Primary Outcome Measures

#### *ECMO patients*

1. Difference of Cytokine response [ Time Frame: 6-24 hours ]

Level of pro- and anti-inflammatory cytokines (IL-1, IL-6, IL-8, IL-10, tumor necrosis factor-alfa) before initiation of ECMO, 2 hours after initiation ECMO support, at explantation of ECMO support, 6-12-24 hours after explantation of ECMO support.

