## 6. Project implementation plan

№ i/n	Name of task, activities for implementation of project tasks	Duration (in months)	Start and end date of work * (dd / mm / yy).	Years of project implementation, expected project results (in terms of tasks and activities)		
				2021	2021	2022
1.	Literature review on treatment of patients with failure of heart and lung within innovation technolog	6 months	01.01.2021-01.06.2021			
1.1	Literature review of patients on ECMO with using extracorporeal cytokine adsorber or hemoperfusion cartridge			Literature review for ECMO patients using an extracorporeal cytokine adsorber and an extracorporeal		

				hemoperfusion cartridge. Obtaining the results of the literary review.		
1.2	Literature review of septic patients with using extracorporeal cytokine adsorber or hemoperfusion cartridge			Literature review for septic patients using an extracorporeal cytokine adsorber and an extracorporeal hemoperfusion cartridge will be conducted. Obtaining the results of the literary review.		
2.	Recruiting patients on ECMO / septic patients with using extracorporeal cytokine adsorber or hemoperfusion cartridge depend of diagnosis	36 months	01.01.2021-31.12.2023	Initial patient condition will be studied	Initial patient condition will be studied	Initial patient condition will be studied
2.1	Examination of patients, verification of diagnosis and other procedure					
2.2	Study of directly clinical results of after using extracorporeal adsorbent on ECMO patients					
2.3	Study of directly clinical results of after using extracorporeal adsorbent on patients with sepsis.					
3.	Clinical and laboratory data will be analyzed on basis of clinical research	12 months	01.01.2023-31.12.2023			A protocol will be developed and optimized for the implementation of

						extracorporeal adsorber technologies for this category of patients
3.1	A protocol for optimization of introduction novel technology will be developed and implemented					
3.2.	Protocol implementation					
4.	Preparation of publications, reports, development of methodological guidelines	24 months	2022-2023		Article in international and local journals	Article in international and local journals
5.	Creation of intermediate and final reports	annually	2021-2023	Interim and final reports will be generated	Interim and final reports will be generated.	Interim and final reports will be generated.

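### The plan does not settle whether ECMO patients may be enrolled after ECMO has started, so the pre-ECMO cytokine sample of the primary outcome is not secured for all of them

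*Combined protocol and SAP*

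**What the plan says.** All references are to the combined protocol and SAP.

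- **Enrolment sentence** (4. Research methods and ethical issues): "Patients before implantation of ECMO and/or patients with sepsis will be enrolled", after written consent. The same section plans cytokine levels before, during and after ECMO.
- **Primary outcome, ECMO patients** (Outcome Measures): cytokines are measured "before initiation of ECMO, 2 hours after initiation ECMO support, at explantation of ECMO support, 6-12-24 hours after explantation of ECMO support".
- **Group labels**: section 4 writes "patients on ECMO – subgroup A", with similar wording for C and E. The Study Design table has "15 patients on ECMO" in each adsorber arm and 15 in the control arm.
- **Eligibility table** (Statistical studies): the row is headed "ICU patients with ECMO". It includes patients by vasopressor support, procalcitonin of at least 1 ng/ml, invasive monitoring and consent. It excludes those under 18, those with acute liver or kidney failure just before transplantation, and those who decline. No item mentions time relative to cannulation.
- **Implementation plan** (section 6): "Recruiting patients on ECMO / septic patients with using extracorporeal cytokine adsorber or hemoperfusion cartridge depend of diagnosis".
- **Analysis** (Statistical studies): quantitative data are compared by Mann-Whitney and t-test. No baseline adjustment is named, and no rule is given for a missing baseline.

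**The concern.** The primary outcome for ECMO patients is tied to the moment ECMO begins, but the plan does not fix whether enrolment comes before that moment. A site that screens from the eligibility table alone could properly enrol a patient who has been on ECMO for days. That patient has no prospective study sample from before ECMO. The plan offers no substitute baseline, no limit on time already spent on ECMO, no use of stored blood and no rule for the gap.

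With 15 ECMO patients per arm there is little room for loss. If the analysis relied on the pre-ECMO value, patients without it would drop out, or baselines taken before and during ECMO would be mixed. Dropping patients for a reason settled before allocation need not bias the comparison of arms. It would cost precision and limit the result to patients who could be enrolled before cannulation.

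The plan also uses several reference points. The ECMO primary outcome starts from ECMO initiation, the d-dimer and lactate outcomes refer back to enrolment, and the inflammatory outcome for septic shock is timed around the adsorber. For ECMO patients, whether the first two coincide depends on the timing left open here.

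**Working it through.** **1. The plan's own count.** 3 arms x 30 = 90, and 6 subgroups x 15 = 90, which matches the stated enrolment. ECMO patients: 3 x 15 = 45. The documents give no alpha, power, effect size or SD, so 90 cannot be derived from a power formula.

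**2. What each place says about timing.**

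| Place | Wording points to | Is it a timing statement? |
|---|---|---|
| Section 4, enrolment sentence | before ECMO | yes |
| Section 4, cytokine plan | samples before, during and after ECMO | on sampling, yes |
| Primary outcome | first sample before ECMO | on sampling, yes |
| Section 4 subgroups; Study Design table | on ECMO | can be read as a label |
| Eligibility row | with ECMO, no timing criterion | label, but nothing excludes patients on support |
| Section 6 | recruiting patients on ECMO | loosely worded, but describes recruitment |

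**3. What follows for one patient.**
- Enrolled before ECMO: both early samples can be taken.
- Enrolled on support within 2 hours of initiation: the first is lost, the second is still possible.
- Enrolled on support after more than 2 hours: both are lost.
- In every case the samples at explantation and 6, 12 and 24 hours later do not depend on enrolment having preceded ECMO.

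**4. Illustration of size.** Assumptions, none of them from the documents: two-sided alpha 0.05, 80% power, one pairwise comparison, SD 1, normal approximation (optimistic at these sizes), and an analysis that needs the pre-ECMO value and drops patients without it.

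Detectable difference = (1.96 + 0.84) x sqrt(2/n per arm).

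| Assumed share enrolled on support | Without pre-ECMO sample, of 45 | Left per arm | Detectable difference |
|---|---|---|---|
| 0% (section 4 governs) | 0 | 15 | 1.02 SD |
| 25% | about 11 | 34/3, about 11 | 1.19 SD |
| 50% | about 22 | 23/3, about 8 | 1.40 SD |

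Other shares behave alike. At 20%, 40% and 60% (n = 12, 9, 6) the detectable difference is 1.14, 1.32 and 1.62 SD. Power for a true difference of 1.0 SD, from Φ(sqrt(n/2) − 1.96), falls from 0.78 at n = 15 to 0.69, 0.56 and 0.41.

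**5. Value of a baseline covariate.** If baseline and outcome correlate at r, adjustment removes a fraction r² of the outcome variance. For an assumed r of 0.5 to 0.7 that is 0.25 to 0.49. This is the general gain from adjustment, not a loss caused by the inconsistency.

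**The case against.** The strongest reply is that there is little conflict. Only the section 4 sentence says when ECMO patients are enrolled, and the primary outcome's schedule agrees with it. Patients enrolled before ECMO are on ECMO when treated, so calling the groups patients on ECMO is natural, and counting how often each wording appears proves nothing. The section 6 line, taken literally, would also mean recruiting patients already receiving an adsorber, which randomisation rules out, so it may be only a work-package title.

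Much of this stands. A reader might infer that the baseline cannot exist. The documents do not support that: if section 4 governs, it can be obtained in everyone. A reader might infer that all patients enrolled on support lose both early samples; those enrolled within 2 hours of initiation lose only the first. A reader might also take the primary analysis to be change from baseline, with arms shrinking accordingly. The outcome is described only as a difference in cytokine response with a list of times, and the named tests can compare arms at each later time.

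What the reply does not remove is that the list a site screens from lets in patients already on support, and that no rule covers those who arrive without the first sample.

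**Conclusion.** The point holds as an unresolved inconsistency with a conditional consequence. The enrolment sentence and the sampling schedule agree with each other. The eligibility table and the implementation plan leave room for enrolment on support. The pre-ECMO sample is lost only for patients so enrolled, and the 2-hour sample only for those enrolled more than 2 hours after initiation.

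The share affected is unknown and is 0% if section 4 governs. The rise from 1.02 SD to 1.19 or 1.40 SD is not an estimate for this trial: it rests on assumed shares and on an assumed analysis that the plan does not specify. The matter is worth settling before recruitment because a sample that was not taken cannot be recovered.

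**What to change.** 1. Reconcile section 4, the Study Design table, the primary outcome, the eligibility table and section 6, stating when enrolment and randomisation take place relative to ECMO initiation. If only patients not yet on ECMO are meant, the eligibility row should say so.
2. Define the analysis baseline for ECMO patients as a cytokine sample at randomisation, before any adsorber starts, in all three arms. Where enrolment precedes ECMO, this is the same as the pre-ECMO sample.
3. Use that baseline as the covariate in the primary cytokine comparison, in place of the unadjusted t-test or Mann-Whitney test, and state in advance how a missing baseline is handled.
4. Keep pre-ECMO values as additional data where they exist.

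The cost is wording changes and at most one sample moved to randomisation. No additional patients are needed.
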